#### **Data collection:**

Study assessments include a battery of pre-post self-report surveys administered at baseline and post-intervention; post-intervention individual exit interviews (conducted via telephone or videoconference), and daily diary surveys and actigraphy assessments (sleep and physical activity) collected for 7 days within the 1-2 weeks before and after the intervention. All study surveys and daily diaries may be completed via REDCap, email, or paper mail, depending on patients' preferences. Data collection will also consist of viewing and extracting data from the EHR of enrolled participants to assess medical and demographic variables (e.g., medical diagnoses, medications, cardiac rehab attendance).

#### **Pre-post survey measures:**

The battery of self-report survey measures will be administered within approximately one week before and after the intervention. This battery will include the following validated self-report surveys: MAIA (body awareness) CAMS-R (attention regulation), EQ (cognitive decentering) DTS (distress tolerance), BVS (interoceptive bias), IUS-12 (ability to withstand uncertainty and ambiguity of future events), ASC (fear of recurrence), the ASI-3 (cardiac anxiety), the Consensus Sleep Diary, the PAVS (physical activity vital sign), Group Cohesiveness Scale, and the Program Satisfaction Survey. The baseline survey will also include questions on the patients' sociodemographic characteristics and medical history. Medical characteristics including SCAD characteristics (e.g., date, pregnancy associated), prior medical history, medical and psychiatric comorbidity, cardiac rehab attendance, and medication will be extracted for the participants' medical records. The pre-post survey battery is included in the IRB submission.

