#### **Daily Diary:**

Participants will be asked to complete a daily diary of abbreviated survey measures for approx. 7 consecutive days during the 1-2 weeks before and after the intervention. To reduce survey burden, the daily diary will consist of 1-2 items from each of the pre-post survey measures; specifically, the items from that had the highest factor loading in the measure's validation study. The evening daily diary will include approx. 10 items. The morning daily diary will include approx. 20 items. In addition, to explore the acceptability of the daily diaries, there will be approx. 2-3 items asking about the experience of completing the daily diary itself (e.g., ease of completion, interference with daily activities). There will be a daily diary assessment each evening which includes items for all of the psychological variables and physical activity, and

there will be a 1-2 items diary assessing sleep quality each morning. Depending on the participant's preference, daily diaries can be completed via REDCap or emailed forms. The daily diary is included in the IRB submission.

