**Measured Outcomes:**

The primary outcomes are feasibility and acceptability of the intervention and research procedures. The exploratory outcomes are changes in psychological and behavioral variables, measured via pre-post intervention surveys, and daily diaries and actigraphy each day for 1-2

weeks before and after the intervention. Daily diaries will include psychological variables and self-reported physical activity (collected at night) and sleep outcomes (collected at morning). Covariates will be extracted from the medical record, including date of SCAD event, pregnancy-associated SCAD, medical and psychiatric comorbidities, cardiac rehab attendance, and hospital readmissions. Please refer to tables 1 and 2 below for details of feasibility and acceptability outcomes (Table 1) and exploratory outcomes (Table 2).

Table 1. PRIMARY OUTCOMES (Aims 1 and 2)	
Feasibility	
Enrollment	≥70% of eligible enroll; <20% ineligible due to each criterion; reasons for ineligibility; reasons for refusal; characteristics of refusers
Retention	≤20% participant attrition
Intervention components	≥70% session attendance; fidelity score ≥70%; ≤20% of sessions missed due to videoconference problems; ≤20% connections dropped during session; number (M≤2.0) and types of videoconference problems
Surveys	≥70% pre-intervention and post-intervention surveys completed; ≥70% daily diaries completed for 7 consecutive days; ≤20% missing data on daily diaries
Actigraphy	≥70% completed 7 consecutive days
Acceptability	
Intervention components	Program satisfaction (M≥7.0), ≥70% plan to use the skills, ≥70% would recommend the program to others ( post-survey ); likes, dislikes, suggestions for program improvement ( exit interview )
Surveys	Ease of survey completion (1=not at all, 10=extremely M≥7.0); level of interference (1=not at all, 10=extremely M≤2.0; post-survey ); experiences, challenges, suggestions for improvement ( exit interview )
Actigraphy	Ease of actigraphy completion (1=not at all, 10=extremely M≥7.0; post-survey ); experiences, challenges, suggestions ( exit interview )

Table 2. EXPLORATORY OUTCOMES (Aim 3)		
Psychological Variables	Measurement	Model Component
Non-judgmental body awareness	Multidimensional Assessment of Interoceptive Awareness	Intervention mechanism
Attention regulation	Cognitive Affective Mindfulness Scale-Revised	Intervention mechanism

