## Analysis Plan

For Aim 1 and Aim 2 will calculate frequencies and proportions and means and standard deviations (or medians and interquartile ranges if variables are non-normal) to assess feasibility and acceptability outcomes. T-tests or chi-square will be used to compare eligible patients who did and did not enroll, and those who enrolled and dropped out, on demographic and clinical variables. Exit interviews will be audio recorded, transcribed, and iteratively analyzed using

thematic content analysis in NVivo 11. Transcripts will be reviewed by two members of the study team to identify themes and develop a coding framework. Discrepancies in coding will then be resolved through discussion.

For Aim 3, we will examine frequency distributions for each exploratory outcome at each timepoint and use non-parametric tests if needed. We plan to use linear mixed effects models with repeated measures and an unstructured covariance matrix to assess changes over time for each psychological and behavioral variable (separate dependent variables). The predictor variables will be time (fixed effect: up to 16 levels across pre-post intervention surveys and daily diaries or actigraphy) and covariates relevant for each dependent variable (random effects). If there are any time effects, we will conduct follow up analyses to determine if those effects show a change over the course of the intervention period in the expected direction. We will create change scores (post-intervention survey minus pre-intervention survey) and explore correlations of changes in psychological variables with changes in behavioral variables. Missing data will be imputed using maximum likelihood estimation and, as a sensitivity analysis, the last observation carried forward. Given the exploratory nature of the proposed pilot study, we will focus the interpretation of Aim 3 analyses on effect sizes (Cohen's d) rather than statistical significance to assess potential signals for intervention effects.

For studies involving treatment or diagnosis, provide information about standard of care at Mass General Brigham (e.g., BWH, MGH) and indicate how the study procedures differ from standard care. Provide information on available alternative treatments, procedures, or methods of diagnosis.

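### Aim 3c takes self-reported sleep change from one survey administration per time point and leaves the repeated morning diary data out of the correlations

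*Combined protocol and SAP*

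**What the plan says.** Four parts of the document bear on this point.

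- **Survey battery.** Under Data collection, the surveys are "a battery of pre-post self-report surveys administered at baseline and post-intervention". Under Pre-post survey measures, "The battery of self-report survey measures will be administered within approximately one week before and after the intervention", and the listed instruments include "the Consensus Sleep Diary, the PAVS (physical activity vital sign"). Table 2 gives the Consensus Sleep Diary as the only self-report source for sleep duration, efficiency and onset latency, alongside actigraphy.
- **Daily diary.** The Daily Diary section has participants complete short measures "for approx. 7 consecutive days during the 1-2 weeks before and after the intervention". Measured Outcomes says that these diaries hold "self-reported physical activity (collected at night) and sleep outcomes (collected at morning").
- **Morning content.** The Daily Diary section describes the morning diary in two ways: about 20 items, and 1-2 items on sleep quality.
- **Analysis.** For Aim 3c the Analysis Plan states: "We will create change scores (post-intervention survey minus pre-intervention survey"), and will then "explore correlations of changes in psychological variables with changes in behavioral variables". It defines no average over diary mornings for this purpose. The daily data do enter the mixed models for change over time, which allow up to 16 levels of time.

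**The concern.** A sleep diary is designed to be repeated, because one night is a noisy guide to a person's usual sleep. A difference between two single administrations carries that noise twice. If the noise is unrelated to the psychological scores, it pulls the Aim 3c correlations between psychological change and sleep change toward zero.

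The plan says that Aim 3 will be read on effect sizes rather than significance. Attenuation therefore acts on the quantity that will be interpreted: a real association between, say, change in fear of recurrence and change in sleep could look negligible. Participants already fill in a morning diary in both windows, so a less noisy score may be available with little extra effort. The rule as written does not use it.

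**Working it through.** **The plan's own figures.** Two survey occasions plus 2 × 7 daily records give 2 + 14 = 16, which matches the stated maximum number of time levels. The plan thus counts each survey as one occasion. Two groups of 8 give 16 participants, and 16 / (1 − 0.20) = 20, which matches the planned enrollment. The correlations would rest on about n=16.

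**Inputs**

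- From the documents: 1 survey administration and about 7 diary mornings per time point; n=16 after the anticipated loss.
- Assumed, because the documents give neither: night-to-night ICC of 0.3-0.5; correlation ρ of 0.5-0.75 between a person's true sleep level before and after.
- Also assumed: the survey version reflects one night; errors on different nights are independent of each other and of the psychological score; the psychological change is measured without error.

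**Formulas**, with total nightly variance set to 1 and k nights averaged per time point:

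- Variance of true change: V = 2 × ICC × (1 − ρ)
- Error variance of the change score: E = 2 × (1 − ICC) / k
- Reliability of the change score: R = V / (V + E)
- Correlation seen when the true value is 0.50: 0.50 × √R

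**Two corners worked out**

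- ICC 0.3, ρ 0.75: V = 2 × 0.3 × 0.25 = 0.15. For k=1, E = 1.4 and R = 0.15/1.55 = 0.10. For k=7, E = 0.2 and R = 0.15/0.35 = 0.43.
- ICC 0.5, ρ 0.5: V = 2 × 0.5 × 0.5 = 0.50. For k=1, E = 1.0 and R = 0.50/1.50 = 0.33. For k=7, E = 0.143 and R = 0.50/0.643 = 0.78.

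| ICC | ρ | R, k=1 | R, k=7 | r seen, k=1 | r seen, k=7 |
|---|---|---|---|---|---|
| 0.3 | 0.50 | 0.18 | 0.60 | 0.21 | 0.39 |
| 0.3 | 0.75 | 0.10 | 0.43 | 0.16 | 0.33 |
| 0.5 | 0.50 | 0.33 | 0.78 | 0.29 | 0.44 |
| 0.5 | 0.75 | 0.20 | 0.64 | 0.22 | 0.40 |

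**Sensitivity**

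- With more stable sleep (ICC 0.7, ρ 0.5-0.7), the true 0.50 appears as 0.32-0.37 for k=1 and 0.46-0.47 for k=7. The gain is smaller but in the same direction.
- With five mornings instead of seven, the two worked corners give R = 0.15/(0.15 + 0.28) = 0.35 and 0.50/(0.50 + 0.20) = 0.71. The correlation seen is then 0.30-0.42, so most of the gain survives some missed mornings.

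**Precision at n=16.** By the Fisher transformation, an observed r of 0.50 has a 95% interval of tanh(0.549 ± 1.96/√13), or about 0.01 to 0.80. The two-sided 5% critical value is 2.145/√(2.145² + 14) = 0.497. The expected r under the 7-morning score (0.33-0.44) is still below it.

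**The case against.** The strongest reply is that the one-night premise is not in the text. The survey form is in the IRB submission and not in this document, and it may ask for recall over several nights. The count of 16 levels shows that a survey is one time level, not how many nights it covers. One could also read the Consensus Sleep Diary as being the morning diary itself, merely listed among the survey instruments; about 20 morning items would fit that. This stands as a limit on the size of the loss. It does not remove the point, because on either reading the Analysis Plan still takes change from surveys alone and gives no rule for turning several mornings into one score.

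Second, a reader might infer that better sleep data are already in hand. The documents do not establish that. If the morning diary holds only 1-2 sleep-quality items, duration, efficiency and onset latency cannot be derived from it. The objection stands until the Daily Diary section is reconciled.

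Third, a reader might extend the criticism to Aim 3b. That fails, because the mixed models already take in the daily data.

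Fourth, the gain is modest. At the two extreme corners the expected r rises by 0.33 − 0.16 = 0.17 and 0.44 − 0.29 = 0.15, less than the sampling error of r at n=16 (about 0.25). Power to detect the association goes from roughly 8-19% to 23-40%, so a miss stays more likely than not. Significance is not the plan's yardstick here, but the imprecision is real.

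**Conclusion.** The point holds for Aim 3c. Followed as written, the plan correlates psychological change with a sleep change based on one administration per time point, and the repeated mornings are left out without explanation. If each administration reflects one night, and under the assumed ICC and pre-post correlation, the correlation seen is roughly half to two thirds of what 7-morning means would give: 0.16-0.29 against 0.33-0.44 for a true 0.50. The loss shrinks if the survey covers several nights or if sleep is more stable than assumed. The gain from averaging shrinks if errors on neighboring nights are correlated.

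This is an improvement to one exploratory analysis in a pilot of about 20 people whose primary outcomes are feasibility and acceptability. It casts no doubt on the sample size or on the Aim 3b models, and the change would reduce attenuation without making the estimates precise. It is worth settling before the data are analyzed, so that survey and diary values are not chosen between once results are known.

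**What to change.** - **Analysis Plan, Aim 3c only.** Define change in self-reported sleep duration, efficiency and onset latency as the mean over the available post-intervention mornings minus the mean over the available pre-intervention mornings. State the minimum number of mornings required in each window and how participants below it are handled.
- **Daily Diary section.** Reconcile the two descriptions of the morning diary, so that it carries the Consensus Sleep Diary items from which the three sleep outcomes are derived.
- **Aim 3b.** Leave the mixed models as they are.

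If the longer morning diary is in use and holds those items, the cost is wording. If the shorter one is in use, participants answer a few more items on about 14 mornings (2 × 7), which works against the plan's wish to limit burden. Mornings already recorded without the items cannot be used this way. Participants below the minimum may also drop out of the correlations, a cost that matters at n=16 and argues against setting the minimum high.

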#### **Daily Diary:**

Participants will be asked to complete a daily diary of abbreviated survey measures for approx. 7 consecutive days during the 1-2 weeks before and after the intervention. To reduce survey burden, the daily diary will consist of 1-2 items from each of the pre-post survey measures; specifically, the items from that had the highest factor loading in the measure's validation study. The evening daily diary will include approx. 10 items. The morning daily diary will include approx. 20 items. In addition, to explore the acceptability of the daily diaries, there will be approx. 2-3 items asking about the experience of completing the daily diary itself (e.g., ease of completion, interference with daily activities). There will be a daily diary assessment each evening which includes items for all of the psychological variables and physical activity, and

there will be a 1-2 items diary assessing sleep quality each morning. Depending on the participant's preference, daily diaries can be completed via REDCap or emailed forms. The daily diary is included in the IRB submission.

**Weekly home practice logs:**

Participants will be given optional weekly home practice logs they can use to track their mindfulness practices throughout the week if they would like to. As part of the intervention, participants will be asked to complete approx. 15-20 minutes of mindfulness practice each day in between study sessions. Participants will be provided with optional weekly home practice logs they can use to record their experience if they would like to. Participants will not be required to submit the log to the study team. Depending on the participant's preference, home practice logs can be completed via REDCap or emailed forms. The home practice log is included in the IRB submission.

We will send participants audio recordings via a secure email link or Dropbox, to help with completing home practice.

**Exit interview:**

Upon completion of the intervention, participants will be asked to complete a 45-60 minute individual exit interview via phone or video conference. These interviews will be audio-recorded for transcription. The exit interview guide is included in the IRB submission.

**Actigraphy:**

An actigraphy device will be used to measure physical activity and sleep patterns. These devices are worn on the wrist. Participants will be asked to wear the actigraphy device daily for up to approximately 7 consecutive days during the 1-2 weeks before and after the intervention. The study team has a set of actigraphy devices which they have pilot tested for participant use in prior studies (Dana Farber Harvard Cancer Center IRB Protocol number 20-170). These devices will be mailed to participants along with detailed instructions (included in this submission) about when and how to wear the devices. Study participants will mail back the devices to the study team upon completion of data collection via return-stamped envelopes. Participants who do not mail back the devices will be sent a follow-up letter asking them to return the device, along with another pre-stamped envelope. All devices will be thoroughly disinfected by study staff between usages to prevent the spread of disease.

We will measure the following outcomes using the actigraphy device:

- a. **Sleep** will be measured continuously for 7 days within the 1-2 weeks before and after the adapted MBCT intervention using actigraphy (wearable wrist device). We will evaluate wear compliance and calculate linear trends in total sleep duration, sleep efficiency, wake after sleep onset, and sleep onset latency over the course of the 8-week intervention (e.g., timings of sleep/awake, timings of being in bed).
- b. **Physical activity** will be measured continuously for 7 days within the 1-2 weeks before and after the adapted MBCT intervention using actigraphy (GENEActiv wearable wrist device). We will evaluate wear compliance and calculate linear trends in moderate-vigorous physical activity, total steps, and sedentary time.

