Cognitive de-centering	Experiences Questionnaire	Intervention mechanism
Distress tolerance	Distress Tolerance Scale	Intervention mechanism
Interoceptive bias	Body Vigilance Scale	FOR process
Intolerance of uncertainty	Intolerance of Uncertainty Scale	FOR process
FOR severity	Assessment of Survivor Concerns	FOR outcome
Cardiac anxiety	Anxiety sensitivity index 3	FOR outcome
Group cohesiveness	Group Cohesiveness Scale	Moderator
Program satisfaction	Program Satisfaction Survey	Moderator
Behavioral Variables	Measurement	Model Component
Sleep duration	Consensus Sleep Diary; Actigraphy	Health behavior outcome
Sleep efficiency	Consensus Sleep Diary; Actigraphy	Health behavior outcome
Sleep onset latency	Consensus Sleep Diary; Actigraphy	Health behavior outcome
Moderate-vigorous physical activity	Physical Activity Vital Sign; Actigraphy	Health behavior outcome
Total steps	Physical Activity Vital Sign; Actigraphy	Health behavior outcome
Sedentary time	Physical Activity Vital Sign; Actigraphy	Health behavior outcome

*Note.* All self-report measures are validated. Variables will be measured pre-post the 8-week intervention, and via daily diaries and actigraphy collected each day during the 1-2 week period before and after the intervention.

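### Actigraphy is planned as a linear trend across treatment but measured only before and after it; no pre-post contrast or Aim 3c change score is defined for it

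*Combined protocol and SAP*

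**What the plan says.** The schedule is consistent throughout. In the Actigraphy section, sleep and physical activity are each "measured continuously for 7 days within the 1-2 weeks before and after the adapted MBCT intervention". Research Design and Methods and Data collection say the same, and the note to Table 2 describes "daily diaries and actigraphy collected each day during the 1-2 week period before and after the intervention". No section schedules wear during the eight weeks of sessions.

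The planned summaries are stated in two places:

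- **Actigraphy section.** For sleep, the team will "calculate linear trends in total sleep duration, sleep efficiency, wake after sleep onset, and sleep onset latency over the course of the 8-week intervention". For physical activity, it will "calculate linear trends in moderate-vigorous physical activity, total steps, and sedentary time", with no period given.
- **Analysis Plan, Aim 3.** The plan uses "linear mixed effects models with repeated measures and an unstructured covariance matrix to assess changes over time for each psychological and behavioral variable". The predictor is "time (fixed effect: up to 16 levels across pre-post intervention surveys and daily diaries or actigraphy", plus covariates. If a time effect appears, "we will conduct follow up analyses to determine if those effects show a change over the course of the intervention period in the expected direction". Interpretation is to rest on Cohen's d more than on significance.

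For Aim 3c, the Analysis Plan defines one change score, the survey after treatment minus the survey before it. Table 2 lists actigraphy as a source for all six behavioral variables.

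**The concern.** A trend over the eight weeks suggests that sleep was followed while participants were in treatment. It was not. A reported slope could be read as gradual improvement session by session, when the data can show only that the two windows differ.

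The Analysis Plan does not settle which quantity is meant. It treats days as categories, leaves the follow-up analyses open and gives no weights or averaging rule for comparing the windows. A Cohen's d for actigraphy needs a defined difference, and none is written down. The unstructured covariance over daily levels is also very large for a study of this size, so the model may not fit as planned.

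In Aim 3c, taken as written, psychological and behavioral change both come from the self-report survey battery. Shared reporting method can make the two look linked. The study collects an objective measure that could serve as a check, but the plan defines no change score from it.

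**Working it through.** **Inputs.** Two actigraphy windows of 7 days (Actigraphy). An intervention of 8 weeks (Adapted MBCT intervention), or 8 × 7 = 56 days. Two groups of about 8, 20% loss and about 20 enrolled (Research Design and Methods). Up to 16 time levels and an unstructured covariance (Analysis Plan). Eight psychological variables, leaving out the two moderators, and six behavioral variables (Table 2).

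**1. The plan's own figures.** Time levels: 7 + 7 + 2 surveys = 16, as stated. Enrollment: 16 / (1 − 0.20) = 20, as stated. Actigraphy alone supplies 7 + 7 = 14 of the levels.

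**2. What is observed.** Scheduled actigraphy days inside the intervention: 0 of 56.

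**3. What a line through both windows measures.** Suppose the outcome is level in each window and differs by D between them. With least squares in calendar time, slope × distance between window centers = D × B / (B + W). Here B is the between-window sum of squares of the day numbers, and W is the within-window sum, 2 × 28 = 56.

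- Windows adjoining a 56-day intervention: centers 63 days apart, B = 14 × 31.5² = 13,891.5, ratio 13,891.5 / 13,947.5 = 0.996.
- Windows one week further out on each side: centers 77 days apart, B = 14 × 38.5² = 20,751.5, ratio 20,751.5 / 20,807.5 = 0.997.

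The day score correlates 0.998 to 0.999 with a plain before/after indicator. The line therefore adds almost nothing to the window difference and cannot test whether change was linear. This assumes calendar time, which the plan does not state. If days were numbered 1 to 14, the correlation would fall to 0.87 and drift within the windows would enter the slope.

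**4. Covariance size.** An unstructured matrix for k levels has k(k + 1)/2 parameters.

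- k = 14: 14 × 15 / 2 = 105.
- k = 2: 2 × 3 / 2 = 3.

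Sixteen people with full wear supply 16 × 14 = 224 daily values, and 20 supply 280. With complete data, the sample covariance of 14 days from n people has rank min(n − 1, 14), so it is singular below n = 15. The plan's 16 to 20 sits just above that. Partial records under maximum likelihood add some information, so this is a guide and not a strict cutoff.

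**5. Aim 3c.** Table 2 gives 8 × 6 = 48 psychological-behavioral pairs. The defined change score supplies survey change on both sides of each pair, and no actigraphy change score is defined for any of them. At n = 16, an observed r = 0.5 has 95% CI tanh(0.549 ± 1.96/√13) = 0.01 to 0.80.

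**The case against.** The strongest reply is that this is largely wording. The Analysis Plan speaks of change across the intervention for surveys and diaries too, which are also collected only before and after. The natural reading is pre-to-post change, and actigraphy is already in the mixed model. By the arithmetic above, a calendar-time slope leads to nearly the same conclusion. About 16 retained participants is above the singularity point of 15, and maximum likelihood can use incomplete records. Aim 3c also refers to behavioral change in general, and Table 2 includes actigraphy there.

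Much of that stands. Pre-post change is plainly intended, and the conclusion would often be the same. It does not supply the contrast, remove the impression of a course observed during treatment, or make 105 covariance parameters comfortable with 16 to 20 people. The mention of behavioral change does not define an actigraphy score when the only formula given uses surveys.

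A reader might go further in four ways that the documents do not support:

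- **That the reported effect will be materially too small,** because the slope is scaled to the eight weeks. The plan never states that scaling.
- **That lines would be fitted inside each window and miss the change.** For sleep, the stated period rules this out.
- **That Cohen's d will be reported only after a time effect.** The condition, "If there are any time effects, we will conduct follow up analyses", governs the follow-up analyses and is not attached to the effect size.
- **That the model will run on only 70% of participants.** That figure in Table 1 is a feasibility threshold, not an expected number of complete cases or an inclusion rule.

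**Conclusion.** The concern holds, at low severity. The planned sleep trend describes a period with no actigraphy (0 of 56 days). In calendar time the fitted line amounts to the pre-post difference (0.996 to 0.997 of it). The Analysis Plan implies that difference without defining it, and its covariance for daily actigraphy (105 parameters, about 16 to 20 people) is at or near the limit of what can be estimated. Aim 3c as written has no actigraphy change score.

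The slope figures assume calendar-day coding, a 56-day gap and a level outcome within each window. The singularity statement assumes complete data. A reader might infer that actigraphy was deliberately excluded from Aim 3c, but the text shows only that its change score is undefined. The primary feasibility and acceptability outcomes and the planned enrollment are not affected.

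**What to change.** - **Actigraphy section.** For both sleep and physical activity, replace the linear-trend wording with the post-window versus pre-window difference, and state which wear days count.
- **Analysis Plan, model.** Name that difference as the actigraphy contrast. Estimate it with a mixed model that has a two-level pre/post factor and a simple covariance; on window means, a two-by-two matrix needs 3 parameters. If daily values are modeled instead, let the pre/post difference vary between participants, so that repeated days are not counted as independent evidence of change. Either form keeps participants who have only one window. Report the contrast with a 95% CI and Cohen's d whatever the overall time test shows.
- **Analysis Plan, Aim 3c.** Add actigraphy change scores (post-window mean minus pre-window mean) alongside the survey change scores.

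The cost is a few sentences and a little analysis time, with no new data or participant burden. Aim 3c gains 48 exploratory correlations with wide intervals: 0.01 to 0.80 for r = 0.5 at n = 16, and wider where windows are missing, because a simple change score needs both. They are a rough check on shared-method association, not a test of it.
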